Sleep disturbance may hinder the rehabilitation process. Clinically significant sleep disturbances after TBI correlate with higher rates of depression, anxiety, pain ([name] DJ, 2012) and fatigue (Englander J, 2010), all conditions which could deter full engagement in rehabilitation. Even in a healthy population a moderate reduction in the amount of quality sleep over time can negatively impact cognitive functions such as behavioral alertness and working memory (Banks S, 2007). BWL exposure has been shown to be effective in both reducing agitated behavior and improving cognition in older adults with dementia (Mishima K, 1994) (Riemersma-van der Lek RF, 2008) (Forbes D, 2011). After TBI, there is an association of sleep problems with more functional limitations, higher reliance on other people for care, and diminished satisfaction with quality of life at one year after injury ([name] DJ, 2012). Improved sleep in the acute recovery phase after TBI may positively impact other rehabilitation outcomes. In the study by Makley, et al. (Makley MJ J.-G. L., 2009) sleep disturbance was associated with longer average length of stay for both acute trauma center (22 days vs. 9 days) and inpatient rehabilitation (37 days vs. 21 days). In non-TBI populations BWL exposure has shown efficacy in the treatment of mood symptoms and improving alertness even with small doses and durations of treatment, such as a single one-hour session (Reeves GM, 2012) (Riemersma-van der Lek RF, 2008) (Revell VL, Jan 2006) (Chang AM, 2012) (Terman M, 2005) (Wirz-Justice A, 2012) (Friedman L, May 2012)

(Neikrug AB, 2012). These additional effects of BWL exposure may provide clinical benefit beyond improved sleep in persons recovering from TBI and will be assessed in the proposed study.

Research and clinical evaluation of sleep often employ actigraphy, which allows for the evaluation of subject movement over time and can be extrapolated to wake/rest cycles (Morgenthaler TI, 2007). Use of actigraphy for sleep evaluation with subjects after brain injury has been successful in both inpatient (Zollman FS C. C., 2010) and outpatient settings (Ayalon L, 2007). Additionally, considerations regarding movements and sleep specific to TBI and actigraph placement, including spasticity and paresis (Zollman FS C. C., 2010), are important and will be considered in the execution of this study.

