Aim 1: In persons with TBI, prospectively compare overnight sleep efficiency in a cohort exposed to morning Bright White Light with a comparison group exposed to Red Light in an acute inpatient rehabilitation setting.

Aim 2: Explore the relationship between Bright White Light exposure during inpatient rehabilitation after TBI and mood, therapy participation, attention, rate of functional recovery and length of stay.

Aim 3: Develop and describe sleep study procedures on the inpatient rehabilitation unit for persons with TBI to support optimal and feasible design of future studies in this important area.

Research Hypothesis:

In persons with TBI, prospectively compare overnight sleep in a cohort exposed to morning Bright White Light with a comparison group exposed to Red Light in an acute inpatient rehabilitation setting.

Hypothesis 1: Individuals exposed to Bright White Light for 30 minutes each morning will have better sleep compared to the Red Light exposure group, as measured by sleep efficiency.

Hypothesis 2: Individuals with daily morning Bright White Light exposure will have better mood (as measured by the Positive and Negative Affective Schedule, PANAS), therapy participation (as measured by a 0-100 therapist rating) and attention (as measured by the Symbol Digit Modalities Test) at 10 days compared to individuals with daily Red Light exposure. The group exposed to Bright White Light will also have less daytime sleepiness and fatigue (as measured by the Karolinska Sleepiness Scale (KSS) and the Barrow Neurological Institute Fatigue Scale (BNI-FS), a faster rate of functional recovery as measured by FIM™ efficiency for the rehabilitation stay and a shorter length of stay compared to those in the Red Light group

Hypothesis 3a: Bright White Light exposure will be rated as a reasonable addition to clinical care by staff using Likert scale ratings. Categorize and quantify rates of any side effects of Bright White Light and Red Light exposure in persons with TBI during inpatient rehabilitation.

Hypothesis 3b: Bright White Light and Red Light exposure will be generally well tolerated with side effect profiles and rates similar to those observed in previous studies with other populations.

[figure not shown]
See Appendix for Flowchart on Specific Aims of this study

V. Study Description

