- [42] **Functional Independence Measure (FIM)** is the most widely accepted functional assessment measure in use in the rehabilitation community. The FIM™ is an 18-item ordinal scale, used with all diagnoses within a rehabilitation population. It is viewed as most practical for assessment of progress during inpatient rehabilitation (State University of New York at Buffalo, 1997) and is assessed as part of normal rehabilitation care at admission and discharge from the rehabilitation unit. FIM™ efficiency is simply the change in FIM™ score divided by the length of rehabilitation stay and is used as marker of relative speed of functional change. We will evaluate for effects on both FIM™ motor and FIM™ cognitive scores.
- **Symbol Digit Modalities Test[43]:** The SDMT is a pencil and paper test for attention that takes approximately five minutes to administer and is frequently used in evaluations after TBI (DeMonte,

2009)) (Kalmar K, 2008) (Hanks R, 2008). The SDMT will be administered at enrollment and after intervention. The Interagency Workgroup on TBI Outcomes selected the Symbol Digit Modalities Test as CORE common data elements in TBI outcomes research.

- Positive and Negative Affect Schedule: The 20-item Positive and Negative Affect Schedule (PANAS), developed with a sample of undergraduate students and validated with adult populations, comprises two mood scales, one measuring positive affect and the other measuring negative affect. Each item is rated on a 5-point scale ranging from 1 = very slightly or not at all to 5 = extremely to indicate the extent to which the respondent has felt this way in the indicated time frame. This scale is used to measure affect over a range of times including: at this moment, today, the past few days, the past week, the past few weeks, the past year, and generally (on average). Watson et al. (Watson, 1988) reported Cronbach's alpha coefficients for the various time reference periods ranging from .86 to .90 for the Positive Affect scale and .84 to .87 for the Negative Affect scale. For the general period, alpha was .88 for Positive Affect and .87 for Negative Affect. Test-retest correlations for an 8-week period ranged from .47 to .68 for Positive Affect, .39 to .71 for Negative Affect (for the general time period, Positive Affect stability = .68, Negative Affect Stability = .71[44]).

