- 3) Clinical Staff feedback: phototherapy intervention will rated using a likert scale on the following categories:

- a. Ease of use
- b. Perceived relevance to rehabilitation care
- c. Impression of effectiveness.

Post Light Therapy Outcome Assessment

Day 13: At the conclusion of the light therapy sessions (and prior to discharge from rehabilitation), a blinded Outcomes Examiner will complete the post therapy outcome assessment. This assessment will include the following:

- Symbol Digit Modalities Test
- Positive and Negative Affect Schedule (PANAS)
- Barrow Neurological Fatigue Scale

XII. Data Analysis

The primary outcome is the between-group difference (BWL vs. RL exposure) in average sleep efficiency at baseline compared to after 10 days of light treatment. ANOVA will be used to compare groups controlling for demographics, injury severity, and use of medications.

Secondary outcomes (mood, therapy participation, attention, daytime sleepiness/fatigue) between groups assessed at baseline and after 10 days of light therapy will be compared using repeated measures ANOVA. FIMTM efficiency and inpatient rehabilitation length of stay will also be compared between groups using ANOVA controlling for the same variables as the primary outcome. Descriptive analysis will summarize responses to the nursing burden questions including estimated staff time for the intervention.

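### FIM efficiency has length of stay as its denominator, and no specified FIM analysis separates faster recovery from earlier discharge

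*Combined protocol and SAP*

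**What the plan says.** - **Section IV, Hypothesis 2** predicts, for the bright white light (BWL) arm, "a faster rate of functional recovery as measured by FIM™ efficiency for the rehabilitation stay and a shorter length of stay". Aim 2, to which this belongs, is worded as exploratory.
- **Section X.D, FIM entry** describes efficiency as "change in FIM™ score divided by the length of rehabilitation stay and is used as marker of relative speed of functional change". The FIM "is assessed as part of normal rehabilitation care at admission and discharge from the rehabilitation unit", so the second measurement moves with the discharge date. The entry ends: "We will evaluate for effects on both FIM™ motor and FIM™ cognitive scores". It states no time point, model or hypothesis for that evaluation.
- **Section XII** says that "FIMTM efficiency and inpatient rehabilitation length of stay will also be compared between groups using ANOVA", with the same covariates as the primary outcome. Those covariates are given as "controlling for demographics, injury severity, and use of medications"; admission FIM is not named. No analysis of FIM gain or discharge FIM is described.
- **Table 1** marks FIM scores and efficiency in the baseline column and in the Day 13 outcome column. This does not match admission/discharge timing.

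**The concern.** Length of stay enters the functional claim twice: as the denominator of FIM efficiency and as what fixes the date of the second FIM. It is also a predicted outcome in its own right. If patients gain FIM points faster early in the stay than late, two patients on the same recovery curve get different efficiencies when one leaves earlier. The earlier leaver scores higher and goes home with less function.

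The trial could then report faster functional recovery when only the stay had changed, and efficiency and stay could look like two separate confirmations of Hypothesis 2. The analysis that would tell these cases apart, discharge FIM given admission FIM, is not specified.

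**Working it through.** **Inputs from the documents.** Efficiency is FIM change divided by rehabilitation stay (X.D). There are 64 per arm (Section VII). The Day 13 assessment comes before discharge (Section XI), so stays are at least 13 days.

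**Inputs assumed, because the documents do not give them.** Two-sided alpha of 0.05, the shape of the recovery curve, the size and spread of FIM gain, the distribution of stays, and any treatment effect on stay.

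**The plan's own figure.** For an effect size of 0.5 and 80% power, the normal formula gives n = 2 × (1.960 + 0.842)² / 0.5² = 62.8, so 63 per arm. The t-based calculation gives 63.8, so 64 per arm and 128 in total, as stated. That figure is for the primary outcome; here it only fixes the group size.

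**Step 1: one curve, two discharge days.** Let gain be G(L) = A(1 − exp(−L/τ)) and efficiency E(L) = G(L)/L. Take A = 50, τ = 20 days, and a stay cut by 20% from 30 to 24 days.

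- Day 30: G = 50 × (1 − 0.2231) = 38.8; E = 38.8/30 = 1.29 points per day.
- Day 24: G = 50 × (1 − 0.3012) = 34.9; E = 34.9/24 = 1.46 points per day.

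Efficiency rises by 12% while gain falls by 3.9 points. The ratio does not depend on A. It is 1.15 for τ = 15, 1.09 for τ = 30 and 1.05 for τ = 60.

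**Step 2: other shapes.** With linear recovery, G = bL and E = b, so the ratio is 1.00 at any stay. With a slow-start logistic curve (midpoint day 21, scale 5 days, A = 60), cutting the stay from 21 to 16.8 days lowers gain from 29.6 to 17.5 and efficiency from 1.41 to 1.04. The sign therefore depends on the curve.

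**Step 3: chance of a significant result.** Simulated trials had 64 per arm and the same exponential curve in both arms:

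- A drawn with mean 50, SD 15;
- stay lognormal, median 28 days, SD of log 0.4, with shorter stays set to 13 days;
- FIM noise SD 6;
- t-test on efficiency, two-sided 0.05.

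| BWL stay | Significant in favour of BWL, τ = 40 to τ = 15 |
|---|---|
| Equal | about 2–3% |
| 15% shorter | about 8% to 24% |
| 20% shorter | about 11% to 39% |

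Mean FIM gain at discharge is about 2 to 3.5 points lower in the BWL arm in the shorter-stay rows. A second set of assumptions (mean stay 25 days, coefficient of variation 0.45, A of mean 60, same minimum stay and noise) gives 33%, 28% and 15% for τ = 15, 20 and 30 with a 20% shorter stay. Gain is then 3.6 to 3.9 points lower. With linear recovery the figure stays at 2–3%.

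**Step 4: precision of a discharge comparison.** The 95% half-width is 1.96 × SD × √(2/64) = 0.346 × SD. For an SD of gain of 12 to 14 points this is 4.2 to 4.8, hence about ±4 to 5 points.

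**The case against.** Several points on the other side stand.

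- **Division alone does not create the effect.** Earlier discharge also shrinks the numerator. A reader might infer that any shorter stay inflates efficiency. The documents give no FIM trajectory to support that, and because patients still in post-traumatic amnesia may be enrolled, a slow start cannot be excluded.
- **The plan does not ignore FIM scores.** A reader might infer that efficiency is the only functional analysis intended. Section X.D does promise motor and cognitive scores. What is missing is narrower: a time point and a model.
- **The 8–39% is not a false-positive rate.** Those scenarios contain a real effect on stay. Stay is tested separately and would itself be significant in about 60–88% of such trials, so a shorter stay would usually be visible. Nor do the documents contain a rule that counts the two results as independent. But seeing a shorter stay does not show whether patients recovered faster or left earlier on the same curve.
- **The 37 and 21 days in Section I are not a treatment contrast.** They are an association between sleep disturbance and stay in a cited study. Patients without sleep disturbance are generally excluded here, so the two figures should not be read as the two arms.
- **Biased discharge is not shown.** Nursing staff may set up the lights and so may know the arm, but no section says that they decide discharge.

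**Conclusion.** The concern holds in a limited form. Hypothesis 2 rests its claim of faster recovery on a ratio whose denominator is another predicted outcome, and Section XII specifies nothing that separates the two. If recovery slows over the stay, a 15–20% shorter stay with no change in recovery would give a significant efficiency advantage in roughly 8–39% of trials, with less FIM gained by discharge. The range rests on assumed exponential curves and an assumed effect on stay. It falls to 2–3% for linear recovery, and a slow-start curve pushes efficiency the other way. The documents do not support saying that the bias will occur or which way it will run; they support saying that the plan could not recognise it. The matter is confined to a secondary, exploratory aim.

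**What to change.** In Section XII, turn Section X.D's promised FIM evaluation into a stated analysis: a between-arm comparison of discharge FIM, motor and cognitive, each adjusted for admission FIM. Report the estimates and 95% confidence intervals beside FIM efficiency and length of stay. State that efficiency and stay are not independent confirmations, and that higher efficiency with a shorter stay will be read as faster recovery only in light of the discharge-FIM estimate and interval.

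Do not make this a rule that the BWL point estimate must not be lower. If BWL patients truly recover faster and leave at equal function, the expected difference is zero. In simulation of that case, about 40% of the significant efficiency results came with a lower BWL point estimate, so the rule would often reject a true effect.

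Reconcile Table 1's Day 13 FIM mark with the admission/discharge timing in Section X.D.

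Cost: a few sentences and two extra models on FIM scores already collected at admission and discharge. The functional claim becomes harder to make, because the discharge-FIM interval will be wide, about ±4 to 5 points under the assumptions above.

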5. Past medical history of narcolepsy
6. Past medical history of bipolar disorder
7. Past medical history of obstructive sleep apnea (OSA)
8. Sleep disturbance defined as having a "0" rating by research staff (using all sources available). If rated a "0" for no sleep disturbance, they must also NOT be receiving sleep medications in the last 72 hours
9. Suspected diagnosis of obstructive sleep apnea (determined by the Berlin Questionnaire)
10. Tetraplegia with less than antigravity strength in all myotomes caudal to C6 level given the limitations on measuring movements with actigraphy in this population (i.e. cannot reliably detect upper extremity or lower extremity movement with this level of paralysis).
11. Current medical orders indicated for night time sleep disruption (e.g. chest PT, MIE q2 hours of meds that disrupt sleep). *May be re-approached if the medical orders are no longer in place.

IX. Rationale for Study Population

The study population of interest is TBI in the setting of acute inpatient rehabilitation, which is typically moderate to severe TBI. Persons less than 18 years of age or greater than 70 years are being excluded from the study because of baseline sleep physiology differences seen in younger and advanced ages. We wish to enroll those with sleep disturbances; those with normal sleep will not be enrolled. We are excluding those who would not benefit from light exposure due to eye abnormalities or those with other pathology that will interfere with sleep and cannot be affected by light exposure. Additionally, since actigraphy relies on limb movement for recording, those with tetraplegia would be excluded.

X. Data Collection and Measures

Screening of subjects will need to occur to determine eligibility of subjects, including review of medical chart. If patients are not eligible or are excluded based on exclusion criteria, no identifiable data is retained. Once consented into the study, the exclusion criteria will be reviewed with the patient and/or their legal representative. Data collection measures, areas assessed, and the timing of when this data is collected is shown in Table 1.

Table 1: Data Collection Measures and Areas Assessed

Measure	Area to be Assessed	Screening and Baseline (Day 0-2)	Intervention (Days 3-12)	Outcome (Day 13)
Demographics	Characteristics (age, education, gender)	X		
Injury characteristics	Cause of injury, date of injury, lowest GCS, PTA/GOAT	X		

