Randomization will occur by research staff member assessing the patient for sleep disturbance, using all sources available, in the first item question from the *Clinician Rating: Delirium Rating Scale – Revised 98* (DelRS-R98) (Trzepacz PT, 2001). Our recent prevalence work showed that 86% of acute TBI admissions have sleep abnormalities using clinician ratings, specifically the DelRS-R98 (Nakase-Richardson R S. M., Prospective evaluation of the nature, course, and impact of acute sleep abnormality following TBI, 2013). Sleep disturbance questions will be asked of the clinical staff whom were involved in caring for the patient during Day 1 of study participation, significant other (if available), and directly of the patient (if possible). The rating will be used as a sleep disturbance severity marker which will be utilized by the statistician during randomization to help control for sleep disturbance severity (Sjösten N, July 2009).

C. Primary Outcome Measure:

Sleep efficiency scores derived from actigraphy data will be the primary outcome, and analysis will be done by [name] at the University of Washington. An Actiwatch 2 (Philips/Respironics, Bend, OR) will be used for study purposes to facilitate consistent measurement across sites. We will set the Actiwatch to record activity data in 60-second intervals. Actigraphy data will be automatically scored with Actiware software (Respironics, Philips Healthcare), which uses validated algorithms to determine whether an epoch of activity is “sleep” or “wake” (Cole RJ, 1992). Typically there is a lack of a consistent sleep/wake cycle in the study population, therefore we will be using sleep efficiency and total sleep time scores obtained during a set night-time interval (2200 to 0600) as the primary index of sleep function, as has been used in previous publications[39, 40]. We will be comparing average between group differences between the BWL and RL groups at baseline and after 10 days of light exposure.

D. Secondary Outcome Measures:

- **Makley Scale:** The Makley scale is a 4-point ordinal scale which allows staff to score sleep as follows: 0 = asleep; 1 = drowsy/falling asleep; 2 = drowsy/waking up; 3 = awake. An hourly sleep log on each patient will be filled out every two hours by the unit nursing staff from 2200 to 0600 hours starting at baseline and through the duration of the study.[41]

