Day 0-1 (2 days): After determining eligibility, the participant will be fitted with an Actiwatch (actigraphy) for continuous monitoring of activity levels both during the day and night (American Sleep Disorders Association, 1995). The Actiwatch will be worn continuously (with removal as needed for hygiene, shower or other clinical care) from enrollment to outcome measurement. Actiwatches will be fully charged and cleared of all previous data before being provided to a subject. Units will be set to record activity data in 60-second epochs. Actiwatches have sufficient built-in memory capacity and battery life to be used for approximately 30 days without recharging. Additionally, sleep logs that rate patient sleep are filled out every hour, between the hours of 2200-0600, this information is then obtained

as completion of the Makley scale. A complete review of symptoms and medical history will be obtained from the subject, LAR, and medical records.

Day 2: Baseline data collection is obtained (See Appendix for Baseline Data Collection Forms). Measures collected include: Symbol Digit Modalities Test, Positive and Negative Affect Schedule (PANAS), Barrow Neurological Fatigue Scale. Clinical Staff, will be asked if there was sleep difficulties and therapist will be asked to rate therapy participation for that day.

Day 2: Randomization. After baseline testing is completed, subjects will be randomized (50:50) using a 2-level stratification design based on two pieces of information:

- 1) Center (U. Washington-Seattle, Baylor-Dallas, Mount Sinai-New York) and
- 2) Severity of Sleep Disturbance using Delirium Rating Scale-Revised 98 Item 1

The rating for the Delirium Rating Scale Item 1 are: 1=Mild, 2=Moderate, 3=Severe

(Nakase-Richardson R S. M., Prospective evaluation of the nature, course, and impact of acute sleep abnormality following TBI , 2013) Using an Access Database, developed by [name] at the University of Washington, centers will randomize the participant into either the Bright White Light Group or the Dim Red Light Group. [46]

Light Therapy:

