Appendix

- Inclusion/Exclusion Checklist
- Makley Sleep Scale Form
- Berlin Questionnaire
- Del-R-98, Question 1 Form
- Functional Independence Measure (FIM)TM
- PANAS
- Karolinska Sleepiness Scale
- Barrow Neurological Institute Fatigue Scale
- Quarterly Staff Survey (a.k.a. Clinician Feasibility Survey)
- Overview of Study Figure

TWILIGHT Study Inclusion and Exclusion Checklist

Inclusion Criteria

Must meet all of the criteria below

- Have experienced a moderate to severe TBI. Defined by any of the following:
 - 1) Loss of Consciousness greater than 30 minutes.
 - 2) Emergency Room admission with a Glasgow Coma Scale of 12 or below.
 - 3) Intracranial abnormalities on imaging.
 - 4) Post-traumatic amnesia that lasts more than 24 hours.
- Admitted to acute inpatient rehabilitation unit at Harborview Medical Center within 3 months of their Traumatic Brain Injury.
- Able to communicate in English.
- Between the ages of 18 and 70 years old

Exclusion Criteria

Unable to enroll if any of the following are true

- Complete blindness
- Absence of eye opening or disorders of consciousness (Rancho level 1-3)
- Does not have sleep disturbance (rating of "0" on item one of the *DeIRS-R98*. If has a rating of "0", but if taking sleep medication in the last 72 hours, then include)
- Tetraplegia with less than antigravity strength in all myotomes caudal to C6 level given the limitations on measuring movements with actigraphy in this population (i.e. cannot reliably detect upper extremity or lower extremity movement with this level of paralysis).
- Past medical history of retinal pathology
- Past medical history of light sensitivity
- Past medical history of narcolepsy
- Past medical history of bipolar disorder
- Past medical history of obstructive sleep apnea
- Suspected sleep apnea. (Determined by administering the Berlin questionnaire)
- Current medical orders indicated for night time sleep disruption (e.g. chest PT, MIE q2 hours of meds that disrupt sleep)". For these subjects, may re-approached if the medical orders are no longer in place.

TWILIGHT STUDY

Was watch verified as on? Staff Initials _____

Date: _____

Makley Sleep Scale Form Clinician rating

Time	Rounding Initials	Sleep Rating Given Observation in the Last Hour (circle)			
2200		0	1	2	3
2300		0	1	2	3
0000		0	1	2	3
0100		0	1	2	3
0200		0	1	2	3
0300		0	1	2	3
0400		0	1	2	3
0500		0	1	2	3
0600		0	1	2	3
Ratings:		Asleep	Drowsy/falling asleep	Drowsy/waking up	awake

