4. Staff says a patient slept fine but family notes the patient was restless overnight, what data do we take for rating of sleep disturbance in the study? **Answer:** Clinically we know that patients/subjects will be observed at different time points and that the type and quality of observations will be variable. Research staff should collect all available data and make their best summary of presence/absence of ANY sleep changes and if present the rating of severity (using the Del-RS-R 98 item 1) considering that this type of data is generally additive to describe what's happened overnight and not necessarily either/or. To score a subject as having no sleep disturbance there should be no clinical data that says the patient didn't sleep perfectly well (i.e. patient/caregiver/family report is all that sleep was fine, no medications given).

BERLIN QUESTIONNAIRE

Height (m) _____ Weight (kg) _____ Age _____ Male / Female

Please choose the correct response to each question.

CATEGORY 1

1. Do you snore?

- a. Yes
- b. No
- c. Don't know

If you snore:

2. Your snoring is:

- a. Slightly louder than breathing
- b. As loud as talking
- c. Louder than talking
- d. Very loud – can be heard in adjacent rooms

3. How often do you snore

- a. Nearly every day
- b. 3-4 times a week
- c. 1-2 times a week
- d. 1-2 times a month
- e. Never or nearly never

4. Has your snoring ever bothered other people?

- a. Yes
- b. No
- c. Don't Know

5. Has anyone noticed that you quit breathing during your sleep?

- a. Nearly every day
- b. 3-4 times a week
- c. 1-2 times a week
- d. 1-2 times a month
- e. Never or nearly never

CATEGORY 2

6. How often do you feel tired or fatigued after your sleep?

- a. Nearly every day
- b. 3-4 times a week
- c. 1-2 times a week
- d. 1-2 times a month
- e. Never or nearly never

7. During your waking time, do you feel tired, fatigued or not up to par?

- a. Nearly every day
- b. 3-4 times a week
- c. 1-2 times a week
- d. 1-2 times a month
- e. Never or nearly never

8. Have you ever nodded off or fallen asleep while driving a vehicle?

- a. Yes
- b. No

If yes:

9. How often does this occur?

- a. Nearly every day
- b. 3-4 times a week
- c. 1-2 times a week
- d. 1-2 times a month
- e. Never or nearly never

CATEGORY 3

10. Do you have high blood pressure?

- a. Yes
- b. No
- c. Don't know

Rating Sleep-Wake cycle disturbance:

Question 1 is utilized in this study

DELIRIUM RATING SCALE-R-98 (DRS-R-98)

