This is a revision of the Delirium Rating Scale (Trzepacz et al. 1988). It is used for initial assessment and repeated measurements of delirium symptom severity. The sum of the 13 item scores provides a severity score. All available sources of information are used to rate the items (nurses, family, chart) in addition to examination of the patient. For serial repeated ratings of delirium severity, reasonable time frames should be chosen between ratings to document meaningful changes because delirium symptom severity can fluctuate without interventions.

DRS-R-98 SEVERITY SCALE

1. Sleep-wake cycle disturbance

Rate sleep-wake pattern using all sources of information, including from family, caregivers, nurses' reports, and patient. Try to distinguish sleep from resting with eyes closed.

0. Not present
1. Mild sleep continuity disturbance at night or occasional drowsiness during the day
2. Moderate disorganization of sleep-wake cycle (e.g., falling asleep during conversations, napping during the day or several brief awakenings during the night with confusion/behavioral changes or very little nighttime sleep)
3. Severe disruption of sleep-wake cycle (e.g., day-night reversal of sleep-wake cycle or severe circadian fragmentation with multiple periods of sleep and wakefulness or severe sleeplessness.)

2. Perceptual disturbances and hallucinations

Illusions and hallucinations can be of any sensory modality. Misperceptions are "simple" if they are uncomplicated, such as a sound, noise, color, spot, or flashes and "complex" if they are multidimensional, such as voices, music, people, animals, or scenes. Rate if reported by patient or caregiver, or inferred by observation.

0. Not present
1. Mild perceptual disturbances (e.g., feelings of derealization or depersonalization; or patient may not be able to discriminate dreams from reality)
2. Illusions present
3. Hallucinations present

3. Delusions

Delusions can be of any type, but are most often persecutory. Rate if reported by patient, family or caregiver. Rate as delusional if ideas are unlikely to be true yet are believed by the patient who cannot be dissuaded by logic. Delusional ideas cannot be explained otherwise by the patient's usual cultural or religious background.

0. Not present
1. Mildly suspicious, hypervigilant, or preoccupied
2. Unusual or overvalued ideation that does not reach delusional proportions or could be plausible
3. Delusional

4. Lability of affect

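### Patients rated 0 for sleep disturbance but on sleep medication are eligible, yet the severity strata run only from 1 to 3 and the sleep-log FAQ rules out such a 0, so their stratum is undefined

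*Combined protocol and SAP*

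**What the plan says.** Four parts of the combined protocol and SAP bear on this.

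- **Eligibility.** Section VIII, exclusion 8, excludes a patient rated 0, with the condition that "they must also NOT be receiving sleep medications in the last 72 hours". The wording is awkward, but the appendix checklist makes the meaning plain. For a patient rated 0 it says "but if taking sleep medication in the last 72 hours, then include".
- **Randomisation.** Section X.B explains the purpose of the rating: "The rating will be used as a sleep disturbance severity marker which will be utilized by the statistician during randomization". Section XI, Day 2, states that "subjects will be randomized (50:50) using a 2-level stratification design based on two pieces of information", namely centre and DelRS-R98 item 1. It then gives the levels: "The rating for the Delirium Rating Scale Item 1 are: 1=Mild, 2=Moderate, 3=Severe". I read the two levels of the design as two factors, not as two grades of severity.
- **Scoring instructions.** The Makley sleep log guidelines (appendix, data collection items 5 and 6) tell staff to look for recent sleep medication and then to rate item 1. FAQ 4 on the same form allows a score of no disturbance only where "patient/caregiver/family report is all that sleep was fine, no medications given".
- **The form itself.** The appended scale runs from 0 (not present) to 3. The anchor for 1 is "Mild sleep continuity disturbance at night or occasional drowsiness during the day". No anchor mentions medication.

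Section XII adjusts the primary ANOVA for demographics, severity of injury and medication use. It names neither centre nor the item 1 rating.

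**The concern.** A stratification factor should have one level for every patient who can be randomised. Here the eligibility rule creates a group that the list of levels leaves out, and the FAQ says that the group should not arise at all. A site that follows the checklist and the scale anchors will reach randomisation with a 0. A site that follows the FAQ will record at least a 1 for the same patient. Both are following written instructions.

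What is at stake is the meaning of the severity stratum. It is there to control for how disturbed sleep is, and under the FAQ rule it also carries some information on medication. Because Section XII does not adjust for the rating, stratification is the only place where the plan controls for it.

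**Working it through.** **1. Eligible ratings against listed levels.**

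| Source | Ratings covered |
|---|---|
| Exclusion 8 and checklist | 0 with sleep medication, 1, 2, 3 |
| Section XI, stratum levels | 1, 2, 3 |
| FAQ 4 | 0 only without medication, so a medicated patient scores 1 or more |
| Scale anchors on the form | 0 to 3, medication not considered |

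The unmatched group is 0 with sleep medication, at each of the three centres. If FAQ 4 governs, the exception in exclusion 8 and the checklist describes a patient who cannot occur. If the exception governs, Section XI lacks a level. FAQ 4 also names no type of medication and no time window, whereas eligibility uses sleep medication and 72 hours. I read the FAQ as meaning sleep medication.

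**2. The plan's own figure.** Section VII gives 128 patients (64 per group) for an effect size of 0.5 and 80% power. The significance level is not stated. With a two-sided 0.05 t-test (assumed), the requirement is 63.77 per group, rounded up to 64, so 128 in total. The figure reproduces, and the point raised here does not change it.

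**3. Possible size of the group.** Section X.B cites 86% of acute TBI admissions with abnormal sleep on this scale. I take the remaining 14% as rated 0. Let *m* be the share of those on sleep medication, which the documents do not give. Eligible patients are the 86% plus the medicated part of the 14%, so the group's share of eligible patients is

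0.14*m* / (0.86 + 0.14*m*).

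| *m* (assumed) | Share of eligible patients | Of 128 |
|---|---|---|
| 10% | 0.014 / 0.874 = 1.6% | 2.1 |
| 25% | 0.035 / 0.895 = 3.9% | 5.0 |
| 50% | 0.070 / 0.930 = 7.5% | 9.6 |
| 100% | 0.140 / 1.000 = 14% | 17.9 |

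**4. Effect of a remedy on the strata.** Three centres by three levels give 9 cells, or 128/9 = 14.2 patients per cell on average. A fourth level gives 12 cells and 128/12 = 10.7 per cell. Pooling a medicated 0 with 1 keeps 9 cells.

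**5. Effect on the analysis model.** Adding centre and a three-level severity factor uses (3 − 1) + (3 − 1) = 4 degrees of freedom.

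**The case against.** The best defence is that the sleep log guidelines already supply a rule. Staff look up recent sleep medication, combine it with everything else known, and only then rate item 1. Read with FAQ 4, this makes medication an input to the rating, so a patient who sleeps well on medication scores at least 1. That fits strata 1 to 3, and it fits Section IX, which does not want normal sleepers enrolled. This is a coherent rule, and a reader should not infer that a medicated patient given a 1 has been mis-rated. What the defence does not remove is the exception in exclusion 8 and the checklist, which expects a rating that the rule would never produce. It also leaves open which of the levels 1, 2 or 3 such a patient receives.

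A second defence is that nothing is harmed. Centre is itself a stratification factor, so differences in rating habits between sites stay within centre and do not unbalance the arms. The primary model also adjusts for medication use. This stands as far as bias is concerned. It does not give the severity factor a single definition.

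Third, the figures in the size table have a weak base. The 86% describes admissions in earlier work, not patients left after this trial's exclusions. If that work scored medicated sleepers as the FAQ does, its 14% holds no medicated patients and the calculation does not apply. This also stands, and it is why only a wide range is offered.

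**Conclusion.** The plan contradicts itself on a stratification factor. Eligibility admits a medicated 0, Section XI lists no level for it, and FAQ 4 says that it cannot occur. No section assigns the group to a stratum.

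The size is about 2 to 18 of 128 patients. This rests on three assumptions: that the cited 86% refers to the same item and a like population, that the other 14% would score 0, and that 10% to 100% of those are on sleep medication. The impact is probably modest.

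Two stronger conclusions may suggest themselves, and the documents support neither.

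- A reader might infer that the Access database would be unable to place such a patient. Its fields and permitted values are not shown, so all that can be said is that the protocol names no stratum.
- A reader might infer that the treatment comparison is biased. Allocation is 1:1 at random within centre whatever severity level is recorded, and the required sample size is untouched.

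What remains is a severity stratum that can be scored in two ways, together with a primary analysis that leaves out both stratification factors.

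**What to change.** Reconcile Section VIII (exclusion 8), Section XI (Day 2), the checklist, the sleep log guidelines with FAQ 4, and the DelRS-R98 form to one scoring rule. Either of two routes closes the gap:

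1. Keep the exception for a medicated 0, define the lowest stratum as *0 on sleep medication, or 1 (mild)*, and amend FAQ 4 so that item 1 is scored without regard to medication.
2. Keep the FAQ rule, delete the exception from exclusion 8 and the checklist, and state which level a medicated patient with no observed disturbance receives.

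Under either route:

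- Use the same medication definition and time window throughout.
- Record sleep medication as its own item, separate from the rating.
- Check that the list of levels in the Access database matches the text.
- Add centre and the same severity levels to the primary ANOVA in Section XII. FIM efficiency and length of stay, which are to use the same covariates, then follow.

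The cost is a few lines of text, a database check and 4 degrees of freedom. Table 1 already collects medication categories at baseline. No patients or procedures are added, and both routes keep the 9 cells.
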